9.4. Exploratory Endpoints

9.4.1. Exploratory Endpoint 1

The exploratory endpoint 1 is the change in mean VAS daily scores from the last week of the SDP to the last week of the DBRW.

The visual analog scale (VAS) of sleep inertia is a self-reported measure that is completed on an electronic hand-held device. The VAS has been used to measure sleep inertia in the context of assessing sleepiness severity at specific time points upon awakening (Hayashi 2005; Takahashi and Arito 2000; Oriyama 2017). Subjects give their indication with a tap on a line that measures how difficult it was to awake each morning with anchors at each end of the line labeled as ‘very easy’ and “very difficult” which correspond to a range from 0 to 100, respectively.

The VAS for sleep inertia will be collected daily from the End of OTTP Visit to the End of DBRW Visit (i.e., each day during the SDP and up through the end of the DBRW).

For each subject the mean of the VAS daily score will be calculated by week (7 day interval) using the daily values from the last 14 days of each period. The mean score for the interval will be calculated by summing the VAS scores over the 7 days and dividing by the number of days where a VAS score was completed.

The change in mean VAS daily scores in the last week will be summarized and analyzed similarly to the primary efficacy endpoint (refer to section 9.1.1).

9.4.2. Exploratory Endpoint 2

The exploratory endpoint 2 is the change in mean of the daily 24-hour TST from the last week of the SDP to the last week of the DBRW.

TST will be a self-reported assessment of sleep periods that is derived from the daily sleep diary. Total sleep time will be collected daily from the End of OTTP Visit to the End of the DBRW Visit (i.e., each day during the SDP and up through the end of the DBRW). This method of reporting TST is used in clinical practice and research in IH (Dauvilliers and Buguet 2005; Dauvilliers 2017), as it provides a measure of sleep in the home environment over a longer period of time than what is feasible within a sleep laboratory.

Items on the questionnaire include:

1. What time did you get into bed?
2. What time did you try to go to sleep?
3. How long did it take you to fall asleep?
4. How many times did you wake up, not counting your final awakening?
5. In total, how long did these awakenings last?
6. Was there anything unusual that affected your sleep last night? (Yes/No) If yes, please explain.
7. What time was your final awakening?
8. What time did you get out of bed for the day?

For each subject the mean daily TST will be calculated by week (7 day interval) using the daily values from the last 14 days of each period. The mean score for the interval will be calculated by summing the TST over the 7 days and dividing by the number of days where TST was completed. Specifically, TST is derived by the following formula:

$$\begin{aligned}
 & [\text{day 1 (Q7-Q2)-Q3-Q5+Q11}] + [\text{day 2 (Q7-Q2)-Q3-Q5+Q11}] + [\text{day 3 (Q7-Q2)-Q3-Q5+Q11}] \\
 & + [\text{day 4 (Q7-Q2)-Q3-Q5+Q11}] + [\text{day 5 (Q7-Q2)-Q3-Q5+Q11}] + [\text{day 6 (Q7-Q2)-Q3-Q5+Q11}] \\
 & + [\text{day 7 (Q7-Q2)-Q3-Q5+Q11}] / \text{number of day completed}
 \end{aligned}$$

The change in mean daily 24-hour TST from the last week of the SDP to the last week of the DBWR will be summarized and analyzed similar to the primary efficacy endpoint (refer to section 9.1.1).

The below parameters will also be descriptively summarized by randomized treatment using the daily values from the last 14 days of SDP and DBRW. For each parameter (with the exception of the number of awakenings [Q4] and naps [Q10]) the mean score for the week (7 day interval) will be calculated by summing each item over the 7 days and dividing by the number of days a response was completed, similar to the TST formula above. Q4 and Q10 are collected as ordinal categories; therefore, the modal response over the 7 day interval will be summarized.

- Sleep Latency (mins) = Q3
- Wake after Sleep Onset (WASO) = Q5
- Time in Bed (TIB) = (Q8-Q1)
- Sleep Efficiency (nocturnal TST / TIB) = $((Q7-Q2)-Q3-Q5)/(Q8-Q1)$
- Number of awakenings = Q4
- Number of naps = Q10
- Total nap duration = Q11
- Nocturnal TST = $(Q7-Q2)-Q3-Q5$

9.4.3. Exploratory Endpoint 3

There will be four exploratory endpoints derived from the WPAI:SHP questionnaire. The validity of the WPAI has been established in a number of diseases (Reilly 1993). The WPAI:SHP measures work time missed and work and activity impairment because of IH during the past 7 days. Specifically, the questionnaire includes the following:

1. currently employed
2. how many hours missed from work due to IH
3. how many hours missed from work other reasons
4. how many hours actually worked
5. degree IH affected productivity while working
6. degree IH affected regular activities, other than work at a job

The change in percent of work productivity and activity impairment from the end of SDP to the last week of the DBRW will be derived for the following four outcomes:

Multiply the below scores by 100 to express in percentage

- Percent work time missed due to IH: Score= $Q2 / (Q2 + Q4)$
- Percent impairment while working due to IH: Score = $Q5 / 10$
- Percent overall work impairment due to IH:
Score= $Q2 / (Q2 + Q4) + [(1 - (Q2 / (Q2 + Q4))) \times (Q5 / 10)]$
- Percent activity impairment due to IH: Score= $Q6 / 10$

The above scores will be derived separately for the end of SDP and end of DBRW. The difference between the two time points represents the change in percent of work productivity and activity impairment. Each outcome will be summarized and analyzed similar to the primary efficacy endpoint (refer to section 9.1.1).

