Jazz JZP080-301	Jazz Pharmaceuticals, Inc Assessment: Work Productivity and Activity Impairment Questionnaire – Idiopathic hypersomnia (WPAI:Idiopathic hypersomnia)										Version Date			
											27MAR2018			
	Date of Assessment										Time of Assessment (24-hour clock)			
	D	D	M	M	M	Y	Y	Y	Y	H	H	:	M	M
Visit				Subject ID						Subject Initials				

**Work Productivity and Activity Impairment Questionnaire:
Idiopathic hypersomnia V2.0 (WPAI: Idiopathic Hypersomnia)**

The following questions ask about the effect of your idiopathic hypersomnia on your ability to work and perform regular activities. *Please fill in the blanks or circle a number, as indicated.*

1. Are you currently employed (working for pay)? _____ NO _____ YES
If NO, check "NO" and skip to question 6.

The next questions are about the **past seven days**, not including today.

2. During the past seven days, how many hours did you miss from work because of problems associated with your idiopathic hypersomnia? *Include hours you missed on sick days, times you went in late, left early, etc., because of your idiopathic hypersomnia. Do not include time you missed to participate in this study.*

_____ HOURS

3. During the past seven days, how many hours did you miss from work because of any other reason, such as vacation, holidays, time off to participate in this study?

_____ HOURS

4. During the past seven days, how many hours did you actually work?

[figure not shown]
_____ HOURS *(If "0", skip to question 6.)*

Jazz 14-005 JZP 110	Jazz Pharmaceuticals, Inc Assessment: Work Productivity and Activity Impairment Questionnaire – Idiopathic hypersomnia (WPAI:Idiopathic hypersomnia)	Version Date
		02APR2015
Visit	Subject ID	Subject Initials

5. During the past seven days, how much did your idiopathic hypersomnia affect your productivity while you were working?

Think about days you were limited in the amount or kind of work you could do, days you accomplished less than you would like, or days you could not do your work as carefully as usual. If idiopathic hypersomnia affected your work only a little, choose a low number. Choose a high number if idiopathic hypersomnia affected your work a great deal.

Consider only how much idiopathic hypersomnia affected productivity while you were working.

[figure not shown]

CIRCLE A NUMBER

6. During the past seven days, how much did your idiopathic hypersomnia affect your ability to do your regular daily activities, other than work at a job?

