7.2.5. Missing and Partial Data

Missing or partially missing concomitant medications and AEs start and stop dates will be imputed as described in **Error! No bookmark name given..** However, imputed dates will NOT be presented in the listings as their sole purpose will be for the classification of the medications as past, concomitant or post (refer to section 8.5) and the classification of the AEs as prior,

treatment-emergent or post (refer to section 10.2).

Missing questionnaire data will be handled as described in the following sections:

- ESS:
 - Individual item scores: section 9.1
 - Total score: section 9.1.2
- Missing data will not be imputed for key secondary endpoints, secondary endpoints, and other secondary endpoints. The handling of missing individual items for IHSS is summarized section 9.2.2. For TST and VAS, daily averages are calculated among non-missing records. Only if all daily values are missing for the last week of the SDP or DBRW, then the subject will be excluded from the comparative efficacy analysis for these endpoints.
- Missing safety data will not be imputed except for AEs and concomitant medication start and stop dates as described above.

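### Applied literally, the SAP's overall work impairment formula returns a missing score for employed subjects who worked no hours and missed some because of IH, although its own value there is exactly 100%.

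*SAP*

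**What the plan says.** SAP 9.4.3 defines four WPAI:SHP outcomes. For "Percent overall work impairment due to IH" it gives one formula, which in plain notation is

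score = Q2/(Q2+Q4) + [1 − Q2/(Q2+Q4)] × Q5/10, multiplied by 100.

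No condition is attached for Q4 = 0 or for a blank Q5. The section lists the six items but does not mention the form's skip instructions.

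The form is in Protocol Appendix 16:

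- Q2 asks "how many hours did you miss from work because of problems associated with your idiopathic hypersomnia".
- Q4 asks "During the past seven days, how many hours did you actually work", with the instruction "If '0', skip to question 6".
- Q5, the item skipped, asks "how much did your idiopathic hypersomnia affect your productivity while you were working".

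On analysis, SAP 9.4.3 states: "Each outcome will be summarized and analyzed similar to the primary efficacy endpoint (refer to section 9.1.1". Section 9.1.1 is an ANCOVA on change from end of SDP to end of DBRW, and it excludes a subject whose score is missing at either time point. On missing data, SAP 7.2.5 states: "Missing data will not be imputed for key secondary endpoints, secondary endpoints, and other secondary endpoints". It has separate provisions for ESS, IHSS, TST and VAS, and none for WPAI. Protocol 9.9.1.4 leaves the definition of the work productivity outcomes to the SAP.

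**The concern.** The form and the formula do not fit together. The form deliberately leaves Q5 blank for a subject who worked no hours, while the formula needs a Q5 value for every subject. SAP 7.1 names SAS, where ordinary arithmetic on a missing operand returns missing, even when the operand is multiplied by zero. An employed subject who lost hours to IH and worked none therefore gets no overall impairment score at that visit, hence no change score, and drops out of this outcome.

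The missingness is driven by the quantity being measured. In a withdrawal trial, the subjects lost could be ones who deteriorated after active drug was stopped. The same subject stays in percent work time missed, so two closely related outcomes would rest on different sets of subjects for no stated reason. SAP 9.4.5 reuses these derivations for the open-label summaries, so the gap carries over to change from the start of the OTTP.

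Elsewhere the SAP does handle structural non-response: non-drivers on IHSS item 14 (9.2.2) and activities not done on the FOSQ-10 (9.3.2). WPAI has no comparable rule.

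**Working it through.** The plan states no figure to reproduce here. The check is to evaluate the formula under the form's own skip rule.

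**Algebra.** Put Q4 = 0 and Q2 > 0. The work-time-missed term is Q2/(Q2+0) = 1, so the weight on Q5 is 1 − 1 = 0. The score is 100 × (1 + 0 × Q5/10) = 100% for every Q5 from 0 to 10. With Q5 blank, a literal program computes 1 + 0 × missing = missing.

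**Cases evaluated.**

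| Q2 | Q4 | Q5 | Formula applied literally | With the rule in the fix |
|---|---|---|---|---|
| 40 | 0 | skipped | missing | 100% |
| 5 | 0 | skipped | missing | 100% |
| 39 | 1 | 0 | 97.5% | 97.5% |
| 39 | 1 | 10 | 100% | 100% |
| 20 | 20 | 5 | 75% | 75% |
| 0 | 40 | 5 | 50% | 50% |
| 0 | 0 | skipped | 0/0, undefined | not calculable |

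A subject who worked one hour is kept at 97.5% to 100%, while one who worked none is lost. Apart from the last row, where no score exists, the only cases lost are those whose score is fixed at the maximum.

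**The other three outcomes when Q2 > 0 and Q4 = 0.** Percent work time missed is still computed, at 100%. Percent impairment while working is properly undefined, since no work was done. Percent activity impairment uses Q6, which the subject still answers.

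**What a loss could do (assumed figures only).** Take 40 employed placebo subjects, of whom k go from 40% to 100% (change +60) while the rest change by +15. The unadjusted mean change with everyone included is [(40 − k) × 15 + k × 60]/40:

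- k = 1: (585 + 60)/40 = 16.1
- k = 5: (525 + 300)/40 = 20.6

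Once the k subjects drop out it is 15.0 in both cases. Other assumptions move it differently. Losing one subject who went from 85% to 100% (change +15) shifts the mean by nothing. Losing one who was at 100% at both visits (change 0) raises it from (585 + 0)/40 = 14.6 to 15.0.

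**The case against.** Four points can be made on the other side.

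**The formula is present, and a sensible programmer would get 100%.** True: the SAP does not omit the formula, and its mathematical value in this case is right. The SAP gives example code for the primary endpoint and PGIc but none for WPAI, so the loss is what a literal implementation produces and is not certain to happen. Still, nothing in the SAP prespecifies the special case, and section 9.1.1 excludes whatever comes out missing.

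**The affected subjects need not have lost the whole week to IH.** This stands. Q3 records hours missed for vacation and other reasons and enters no formula. A subject with 5 hours missed for IH, 35 for vacation and none worked also has Q2 > 0 and Q4 = 0. A reader might infer that those who drop out are simply the most impaired subjects. The documents support only that their score, as the SAP defines it, is the maximum.

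**Size and direction are not established.** This also stands. A reader might assume that other employed placebo subjects average 45% at end of DBRW and that 3%, 5% or 10% are lost, and so infer a bias of 55 × 0.03 = 1.65, 55 × 0.05 = 2.75 or 55 × 0.10 = 5.5 points. That is a shift in one arm's end-of-DBRW mean. It is not bias in the planned comparison, which is a difference in change adjusted for the end-of-SDP score, and which becomes a rank analysis with a Hodges-Lehmann estimate if the residuals fail the Shapiro-Wilk test. Bias toward no difference needs the lost subjects to be mainly on placebo with above-average worsening. A missing score at end of SDP, before randomized treatment, also removes a subject and can occur in either arm.

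**Little depends on it.** The outcome is exploratory and outside the testing hierarchy in SAP 7.4, and part of the information survives in percent work time missed and in Q6.

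**Conclusion.** The point holds as a scoring defect in one of the four WPAI outcomes. Read literally, SAP 9.4.3 and the skip rule in Protocol Appendix 16 together discard a score that the formula itself fixes at 100%, and they do so because of the outcome. Assigning 100% is the formula's own result and not imputation, so the silence of SAP 7.2.5 on WPAI does not stand in its way.

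The comparison on this outcome could be biased: toward no difference if such subjects arise mainly on placebo after withdrawal and worsen more than the rest. The documents give no employment rate, no count of subjects with Q2 > 0 and Q4 = 0, and no WPAI values, so neither the size nor the direction can be stated. The conclusion rests on ordinary SAS arithmetic being used without a special case. The primary and key secondary conclusions are not touched. This is a minor correction.

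**What to change.** Add to SAP 9.4.3:

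1. If Q1 = yes, Q2 > 0 and Q4 = 0, overall work impairment is 100%. State that this is the formula's value, consistent with percent work time missed of 100%. State also that Q3 enters neither formula, so weeks partly lost to other reasons are scored the same way.
2. If Q2 = Q4 = 0, percent work time missed and percent overall work impairment are not calculable (0/0).
3. The same rules apply to the open-label summaries in SAP 9.4.5.

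The cost is a few lines of SAP text and the matching condition in the derivation program. No new data are needed. No calculable score changes, and percent impairment while working and percent activity impairment stay as they are.

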9.4.4. Subgroup Analyses

Subgroup analyses for groups specified in section 7.5 will be performed for the primary and key secondary efficacy endpoint using mITT.

These subgroups will be analyzed similarly to the primary and key secondary efficacy analysis with the exception that for the Baseline Medication Group subgroup analyses, the Baseline Medication Group fixed effect will be excluded from the ANCOVA models. Normality assumptions will not be reassessed for subgroups. The corresponding parametric or nonparametric analysis used for the overall sample will be applied to each subgroup.

For each primary and key secondary efficacy endpoint, a forest plot summarizing the treatment difference and 95 % CI will be provided by each subgroup with sufficient sample size.

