5.5. Randomization and Blinding

An Interactive Web Recognition System (IWRS) vendor will prepare and retain the master randomization code for the entire study. The IWRS vendor will not be involved in the analysis of this study.

At the end of the SDP, subjects meeting randomization criteria will be randomized via IWRS 1:1 to either JZP-258 at the stable dose established in the previous 2 weeks or to Placebo at a volume equivalent to the JZP-258 dose that was established in the previous 2 weeks. Randomization will be stratified by the subject's use of stimulant agent and / or Xyrem at baseline per the following baseline medication group:

Group 1: subjects on Xyrem only

Group 2: subjects on Xyrem and an additional stimulant or alerting agent

Group 3: subjects not currently taking Xyrem but are taking a stimulant or alerting agent

Group 4: subjects not currently taking Xyrem or a stimulant or alerting agent.

A double-blind approach will be used during the DBRW. JZP-258 and JZP-258 placebo oral solution will be matched in volume, to ensure adequate blinding of the subject and study personnel. The Jazz study team, with the exception of the Jazz clinical trial material supply group will remain blinded until the formal database snapshot for the final comparative efficacy analysis.

During the DBRW a subject's treatment assignment should only be unblinded when knowledge of the treatment is necessary for immediate medical management of the subject. In the case of an immediate medical emergency, an Investigator or his / her designee will be able to unblind a subject at any time via the IWRS without any obligation to contact the Medical Monitor prior to emergency unblinding. The Investigator or his/her designee is responsible for all decisions

related to medical treatment in the study. A comment must be entered in the source documentation to specify the reason for unblinding, along with the date on which the code was broken and the identity of the person authorizing the unblinding. Subjects for whom the blind is broken will be withdrawn from the study. The Medical Monitor should be notified of the unblinding as soon as possible, but the results of the unblinding should not be disclosed to the Medical Monitor.

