7.1. General Methods

Analyses and summary outputs will be generated using SAS® version 9.4 (or higher). Categorical variables will be presented using counts and percentages. Unless otherwise specified, continuous data will be summarized using descriptive statistics comprising of the number of subjects with data to be summarized (n), mean, SD, median, minimum (Min) and maximum (Max).

For quantitative measurements, change from baseline will be calculated as:

- Change from baseline = Test value at visit X – baseline value

Unless otherwise specified, analyses based on mITT or DBRW SAF that intends to compare the two randomized treatment groups or to summarize the data during DBRW will be presented by randomized treatment group. In general, other analyses will be summarized by baseline medication groups. Summaries by baseline medication group (as defined in the electronic database) and baseline medication subgroup of efficacy analyses will be combined if there are too few subjects in any group.

- Group 1 and Group 2 will be combined if there are less than 10 subjects in either group and outputs will be summarized by Group 1 or 2 vs Group 3 vs Group 4.
- If the combined total of Group 1 and Group 2 is less than 10, then Groups 1, 2, and 3 will be combined. In this case, outputs will be summarized by Group 1 or 2 or 3 (Receiving Baseline IH Medication) vs Group 4 (Treatment Naïve).

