7.5. Subgroups and Subgroup Analyses

Subgroup analyses will be conducted on the primary and key secondary efficacy endpoints for the following:

- Baseline Medication Group, if data are too sparse for at least one of the groups, then groups will be pooled (refer to section 7.1).
- JZP-258 stable dose regimen (e.g. once nightly vs twice nightly)
- Gender
- Region (North America vs Europe)
- High enrolling sites, based on the number randomized (Site XXX, Site XXX, vs all other)
- Baseline median BMI (kg/m^2) (\leq median vs $>$ median)
- Idiopathic Hypersomnia diagnosis (Long sleep vs without long sleep)
- With regard to COVID-19 considerations, Type of Visit (On-site vs Remote): On-site is defined as having both end SDP and end DBRW visits performed on site; Remote is defined as having at least one remote visit for either end SDP or end DBRW visit.

Should there be less than 20 subjects in any subgroup, then only summary statistics would be presented. The exception to this is the subgroup analysis for on-site vs remote; this subgroup analysis will be performed irrespective of subject numbers.

The output for estimating the treatment difference within subgroup will not be provided (least square [LS] means, standard error [SE], LS Mean Difference (95% confidence interval [CI]) or median difference (95% CI) and p-value) if the data are too sparse.

It should be noted that the study was not designed to detect treatment differences with high statistical power within any subgroups.

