9.1.1. Primary Endpoint Analysis

For the main analysis of the primary efficacy endpoint, an analysis of covariance (ANCOVA)

will be performed using the PROC MIXED SAS procedure. The model will include the change in ESS from the end of the SDP to the end of the DBRW as the dependent variable; the treatment group and baseline medication group as fixed effects as well as the ESS score at the end of SDP as a covariate. If the ESS total score at the SDP and/or DBRW is still missing after the imputation of ESS item value as specified above, the subject will be excluded from the primary analysis.

All group comparisons from the ANCOVA model will be based on Type III sum of squares. Least square mean (LS mean) and standard error (SE) will be provided for each treatment group. The difference between these two LS means along with the SE of the difference, 95% confidence interval (CI) and associated p-value corresponding to testing the hypothesis of no difference between the treatment groups will also be provided.

The normality assumption of the ANCOVA model will be examined by residual analysis using the Shapiro- Wilk test at a 0.05 significance level. If the normality assumption is considered violated, a non-parametric ANCOVA with the covariate and response variables replaced by their ranks (Conover and Iman 1982) will be used for the primary efficacy analysis of the primary efficacy endpoint. In the event of ties in the baseline or change from baseline, average ranks will be used. The ranks will be used in the ANCOVA with the rank for the change from baseline as the dependent variable, treatment and baseline medication group as fixed effects, and the rank for ESS score at the end of SDP as a covariate. P-values will be presented from the rank based ANCOVA. The estimated median difference between the change in ESS between the two treatment groups and asymptotic 95% confidence intervals will be presented using the Hodges- Lehman estimator (Hodges and Lehman 1962).

A box plot of the change in ESS from the end of the SDP to the end of DBRW by randomized treatment group will be presented.

Example SAS Code for the ANCOVA model is shown below.

PROC MIXED DATA =ANAL METHOD =TYPE3;

CLASS TRT03PN BMED;

MODEL CHG = TRT03PN BASE BMED/ RESIDUAL OUTP=RESIDUAL;

LSMEANS TRT03PN/DIFF CL;

RUN;

The SAS code below evaluates the assumption of normality for the residuals from the above ANCOVA model using the Shapiro Wilk test.

PROC UNIVARIATE DATA=RESIDUAL NORMAL;

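### SAP 9.4.4 drops the stratification factor from the baseline-medication subgroup ANCOVAs even where pooling puts two or three randomization strata into one subgroup

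*SAP*

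**What the plan says.** - **Stratification.** SAP 5.5 stratifies the 1:1 randomization by "use of stimulant agent and / or Xyrem at baseline per the following baseline medication group". There are four groups: Xyrem only (1), Xyrem plus a stimulant or alerting agent (2), a stimulant or alerting agent without Xyrem (3), and neither (4).
- **Primary model.** SAP 9.1.1 fits "the treatment group and baseline medication group as fixed effects as well as the ESS score at the end of SDP as a covariate". SAP 9.2.2 analyses IHSS in the same way.
- **Subgroup models.** SAP 9.4.4 repeats the primary and key secondary analyses within each subgroup, with one exception: "for the Baseline Medication Group subgroup analyses, the Baseline Medication Group fixed effect will be excluded from the ANCOVA models".
- **Pooling.** SAP 7.5 lists the subgroup as "Baseline Medication Group, if data are too sparse for at least one of the groups, then groups will be pooled", and refers to 7.1. SAP 7.1 has two rules: "Group 1 and Group 2 will be combined if there are less than 10 subjects in either group"; and "If the combined total of Group 1 and Group 2 is less than 10, then Groups 1, 2, and 3 will be combined".
- **Minimum size.** SAP 7.5: "Should there be less than 20 subjects in any subgroup, then only summary statistics would be presented".
- **Status.** SAP 7.4 places subgroup results outside the testing hierarchy, with nominal p-values. SAP 7.5 notes that the study was not designed for high power within subgroups.

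**The concern.** The exclusion in 9.4.4 has no condition attached. It fits an unpooled subgroup, where every subject is in the same stratum and the term cannot be estimated. After pooling under 7.1, the subgroup contains two or three strata, the term varies within it, and 9.4.4 still removes it. The drop rule and the pooling rule were never joined.

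The plan then treats like cases differently. The subgroups by gender, region, BMI, site, dose regimen, diagnosis and visit type also mix strata, and they keep the term because they follow the primary model. A pooled medication subgroup would be the one multi-stratum entry for ESS and IHSS with no adjustment for the factor used to randomize.

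At stake are a somewhat wide confidence interval and a chance arm imbalance within a small stratum left uncorrected, both in a subgroup display. For the pool of Groups 1, 2 and 3 there is a reason to expect the strata to differ. Under Protocol 4.1, only subjects not on Xyrem need an ESS of 11 or more at entry. Under Protocol 4.3.3, Xyrem subjects may be randomized with no change on PGIc, while the others need improvement and a lower ESS. This argument does not separate Groups 1 and 2, which follow the same rules.

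**Working it through.** **Inputs.** The SD of 5.5, the 3.5-point effect and 56 subjects per arm are from SAP 5.4; the pooling and size thresholds are from SAP 7.1 and 7.5. The documents give no expected stratum sizes or stratum means, so those below are assumptions.

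**The plan's own figure.** The plan states no figure for the subgroup models. Its overall power does reproduce: 3.5 / (5.5 × √(2/56)) = 3.367, and Φ(3.367 − 1.960) = 92.0% for a fixed design, or 91.8% with the planned interim look at 60% information, as stated. The point does not rest on this; it only confirms how the SD is used.

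**Can a pooled subgroup reach the model?** Yes, under both rules.
- Group 1 = 8 and Group 2 = 12: one group is below 10, so they are pooled; the total of 20 is modelled with two strata.
- Groups 1 and 2 = 8 together and Group 3 = 32: all three are pooled; the total of 40 is modelled with three strata.

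A pool of 10 to 19 subjects gets summary statistics only.

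**Loss of precision.** If two strata with shares p and 1 − p differ by d in mean change, leaving the term out adds p(1 − p)d² to the residual variance. To a large-sample approximation, SE inflation = √(1 + p(1 − p)d² / 5.5²) − 1, with 5.5² = 30.25.

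| Mix | p(1 − p) | d = 1 | d = 2 | d = 3 |
|---|---|---|---|---|
| 30:70 | 0.21 | 0.35% | 1.4% | 3.1% |
| 50:50 | 0.25 | 0.41% | 1.6% | 3.7% |
| 9 of 64 | 0.121 | 0.20% | 0.8% | 1.8% |

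The first two rows concern the pool of Groups 1 and 2. The 30:70 mix is reachable (9 and 21). The 50:50 row is a limit: with one group below 10 and at least 20 in total, the most even mix is 9 and 11, which gives 0.4%, 1.6% and 3.6%. The third row is for the pool of Groups 1, 2 and 3, which forms only with at most 9 Xyrem users; it treats Groups 1 and 2 as one stratum and assumes 55 subjects in Group 3.

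**Chance imbalance.** Suppose the 9 Xyrem users split 6:3 and the 55 others 27:28, giving arms of 33 and 31. A 3-point stratum difference then moves the treatment estimate by 3 × (6/33 − 3/31) = 0.26 ESS points. The standard error is 5.5 × √(1/33 + 1/31) = 1.38, so the shift is about 0.19 of it.

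**Simulation.** Pools of 8+12, 8+32 and 4+4+32 were fitted with and without the stratum term: allocation balanced within strata, residual SD 5.5, 4,000 runs per setting.
- The average error of the estimate without the term never exceeded 0.06 points.
- The standard error rose by 0.6-1.7% at a 2-point stratum difference, 2.6-6.9% at 4 and 6.2-15.0% at 6.
- At 6 points the nominal type I error fell to about 0.03, and power for a 3.5-point effect fell by about 7 percentage points at most (0.26 to 0.19 with 20 subjects; 0.48 to 0.41 with 8+32).
- With no stratum difference, the two models' standard errors agreed within 0.2%.

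**The case against.** The case for leaving the text alone has several parts.

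- **Several conditions must coincide.** Pooling must be triggered, the pool must reach 20 subjects, and the strata must differ after adjustment for the end-of-Stable-Dose score, which stays in the model. No passage shows that mean change on withdrawal differs by stratum. This stands, and it is why the point is minor.
- **The rank branch limits the effect.** If normality is rejected overall, SAP 9.4.4 carries the rank analysis into every subgroup. The reported median difference and CI are then Hodges-Lehmann, coded in SAP 9.1.1 with treatment and change only. The stratum term would affect just the nominal p-value. This stands.
- **A reader might infer that PGIc is handled correctly in the same pooled subgroup, so that ESS and IHSS are the odd ones out.** The documents do not support that contrast. In SAP 9.2.1 only the CMH p-value is stratified; the code for the difference and its CI has no stratum. That the CMH test stays stratified in a pooled subgroup is itself inferred from silence in 9.4.4.
- **A reader might infer a biased treatment effect.** Stratified 1:1 randomization is meant to keep the arms balanced within strata, so on average the omission costs precision and is conservative. The 0.26-point shift needs an assumed 6:3 split.
- **Strata judged too sparse to show separately need not each have a term.** This is defensible in a descriptive display. But the plan does not give it as a reason, and it keeps the same sparse strata as terms in every other subgroup.

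**Conclusion.** The gap in the text is real and its consequence is small. As written, a pooled baseline-medication subgroup would be modelled for ESS and IHSS without the factor used to randomize, unlike every other multi-stratum subgroup. In the parametric branch this touches the LS-mean difference, its CI and its p-value; in the rank branch, only the nominal p-value.

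For assumed stratum differences of 1 to 3 ESS points, the standard error is at most about 3.7% too large for a pool of Groups 1 and 2, and about 1.8% for the 9-of-64 pool of three groups. Larger losses need stratum differences of 4 to 6 points, which exceed the 3.5-point treatment effect the trial was powered for. These sizes rest on the assumed stratum sizes and differences, and on 5.5 as the residual SD.

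A reader might go further and infer that the primary or key secondary tests are affected. They are not: SAP 9.1.1 keeps the baseline medication group in the primary model, and subgroup results lie outside the hierarchy.

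**What to change.** In SAP 9.4.4, state that the Baseline Medication Group effect is excluded only when the subgroup is a single randomization stratum. Where groups are pooled under 7.1, keep the randomization stratum as a fixed effect in the subgroup's ANCOVA or rank ANCOVA.

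The cost is one clause, plus one degree of freedom for a two-stratum pool or two for a three-stratum pool, in a subgroup that must already have at least 20 subjects. If the sponsor prefers to omit the term because the strata are sparse, the SAP should say so. Either way, settle it before the unblinding described in SAP 5.6, so that the model is not chosen after the data are seen.
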